1. PROTOCOL SUMMARY

1.1. Synopsis

Protocol Title: A randomized, double-blind, placebo-controlled, three-period two-treatment incomplete-block crossover study to investigate the effects of intravenous GSK3858279 on a battery of evoked pain tests in healthy participants.

Short Title: GSK3858279 vs PBO, Phase 1, Evoked Pain Tests, Pharmacokinetics and Target Engagement in healthy participants.

Rationale: The purpose of the study is to elucidate the mechanistic basis for the analgesic effects of GSK3858279 in humans by using a battery of experimental pain assessments in healthy participants.

Objectives and Endpoints:

Objectives	Endpoints
Primary	Primary
To evaluate the effects of IV administration of GSK3858279 in Ultraviolet B (UVB) burn inflammatory test, cold pressor test and electrical pain test in the PainCart	UVB heat pain detection (°C) Cold pressor time to intolerable pain threshold (sec) Electrical pain tolerance threshold (mA) - single stimulus
Safety	Safety
To evaluate the safety and tolerability of GSK3858279 following IV dosing	Adverse Events (AE) and Serious Adverse Events (SAE). Clinical laboratory measurements, 12-lead electrocardiograms (ECG) and vital signs that are considered of potential clinical importance.
Exploratory	Exploratory
To evaluate the pharmacokinetics (PK) of GSK3858279 following IV administration	Serum PK concentrations and parameters including but not limited to: area under the concentration-time curve [AUC], maximum concentration [Cmax], t _{max}
To evaluate the target engagement (TE) of Chemokine C-C motif ligand 17 (CCL17) by GSK3858279 following IV administration	Free and total CCL17 levels in serum
To evaluate the effects of IV administration of GSK3858279 in additional endpoints in UVB test, cold pressor test and electrical pain test in the PainCart	Heat pain detection on normal skin (°C) Cold pressor time to pain detection (sec) Electrical pain detection (mA) - single stimulus Electrical pain detection and tolerance threshold (mA) - repeat stimulus

Objectives	Endpoints
	For each test Area Under the Curve (AUC)/Area Above the Curve (AAC) and post-test eVAS
To evaluate the effects of IV administration of GSK3858279 in pressure pain test and Conditioned pain modulation (CPM) test of the PainCart	Pressure pain (tolerance and detection) - KPa CPM - (detection and tolerance threshold) – mA For each test AUC/AAC and post-test eVAS
To assess the potential for anti-GSK3858279 antibody formation following IV dosing	To include: incidence, titres, and, for samples with confirmed anti-drug antibodies (ADAs), neutralising activity

Overall Design:

This is a single-centre, randomized, double-blind, placebo-controlled, three-period two-treatment incomplete-block crossover study to investigate the effects of intravenous GSK3858279 on a battery of evoked pain tests in healthy participants.

Disclosure Statement:

This is a cross-over, basic science study with three study periods that is masking the participant and investigator.

Number of Participants:

A maximum of 30 healthy male participants will be enrolled into the study, such that at least approximately 24 participants complete dosing and critical assessments in all three study periods.

An interim analysis may be performed once the last UVB-MITT participant has completed their period 3 final day 15 PainCart assessments. An interim analysis may also be performed once the final participant has completed their period 3 final day 15 PainCart assessments.

For both UVB Heat Pain Detection and Cold Pressor time to intolerable pain threshold, the sample size is higher than that required for the Electrical Pain tolerance threshold test. Therefore, for the UVB-exposed population, from here on referred to as the UVB-MITT population, approximately 18 participants are required to be enrolled to ensure that approximately 15 participants complete all UVB tests of the PainCart assessment on irradiated skin in all three study periods.

Note: "Enrolled" means a participant's, or their legally acceptable representative's, agreement to participate in a clinical study following completion of the informed consent process. Potential participants who are screened for the purpose of determining eligibility for the study, but do not participate in the study, are not considered enrolled, unless otherwise specified by the protocol.

In each study period participants will receive either GSK3858279 or placebo in a 1:1 ratio. During the trial, participants will receive both treatments, either two doses of GSK3858279 and one dose of placebo, or two doses of placebo and one dose of GSK3858279 with equal likelihood. The order of treatment assignments will be randomized.

If participants prematurely discontinue the study, additional replacement participants may be randomized at the discretion of the Sponsor and in consultation with the Principal Investigator in order to ensure sufficient participants complete the study. Replacement participants will be assigned to the same treatment sequence as the participant they are replacing, at the discretion of the Sponsor and in consultation with the Principal Investigator.

Intervention Groups and Duration:

The study duration, including screening and follow-up will be approximately 6 months for all participants in the study:

Screening	Approximately 28 days prior to first dose.
Number of Participants	One Cohort of a maximum of 30 participants (N=30)
Study (Treatment) Period(s)	Will comprise of three study periods, investigating the difference between GSK3858279 (3mg/kg IV) and Placebo in the PainCart assessments. Each participant will be admitted to the unit either two days before dosing (Day-2, UVB-MITT participant) or one day before dosing (Day-1, non-UVB-MITT participant) on each study period. Participants will be dosed on Day 1 and discharged on Day 2 (except if, for medical reasons, participants need to stay longer). The participants will return for an outpatient visits on Day 7 (UVB-MITT participants only), Day 8 and Day 15. The participants will be contacted on Day 25 and asked about their general health.
Washout Period	Will be at least 4 weeks between doses for an individual participant.
Follow-Up	The participants will be contacted on Day 36 by telephone and asked about their general health. Approximately 56 days after the last study administration, a final follow-up visit will occur. If warranted, additional follow-up visits may be scheduled.

Data Monitoring or Other Committee:

There will not be a data monitoring committee or any other committee on this study.

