4.2. Number of Participants

Thirty healthy male participants will be enrolled into the study, such that at least approximately 24 participants complete all activities with the exception of the UVB on irradiated skin assessments, in all three study periods. If participants prematurely discontinue the study, additional replacement participants may be randomized, in order to guarantee that sufficient participants complete all three study periods. Replacement participants will be assigned to the same treatment sequence as the participant that they are replacing, at the discretion of the Sponsor and in consultation with the Principal Investigator.

Of the maximum thirty to be enrolled, approximately 18 healthy male participants are to be enrolled as part of the UVB population such that approximately 15 subjects complete the UVB heat pain detection test of the PainCart assessment on irradiated skin in all three study periods, in addition to the rest of the assessments.

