6.3. Measures to Minimize Bias: Randomization and Blinding

6.3.1. Randomization

At Screening a unique Participant Number (case report form [CRF] number) will be assigned to any participant who has at least one Screening procedure performed, other than informed consent. The unique Participant Number will be used to identify individual participants during the course of the study.

Participants who meet the screening eligibility criteria will be randomized to a treatment group through RAMOS NG. The randomization is centrally controlled by RAMOS NG.

RAMOS NG will confirm the participants CRF number (Participant number) and provide the randomization number, where:

- A randomization number will be assigned from a randomization schedule generated by Clinical Statistics, prior to the start of the study, using validated internal software. Once assigned, this number must not be reassigned to any other participant in the study.

In each period participants will receive either GSK3858279 or placebo in a 1:1 ratio where the intervention codes are as follows:

Intervention code	Intervention Description
A	3 mg/kg IV GSK3858279
P	Placebo

During the trial, participants will receive both treatments, either two doses of GSK3858279 and one dose of placebo, or two doses of placebo and one dose of GSK3858279 with equal likelihood, the order of treatment assignments will be randomized. The exact sequences will be blinded to the blinded investigator site staff and participants to prevent bias. Participants will be randomized to a specific sequence on Day 1 of the first study period.

The randomization will be stratified based on whether the pain assessments will be performed in the morning or afternoon.

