6.3.2. Blinding

This will be a double-blind study with respect to allocation of GSK3858279 or placebo to participants and the following will apply.

- The investigator or treating physician may unblind a participant's intervention assignment **only in the case of an emergency** OR in the event of a serious medical condition when knowledge of the study intervention is essential for the appropriate clinical management or welfare of the participant as judged by the investigator.
- The interactive voice response system (IVRS)/ interactive web recognition system (IWRS) will be programmed with blind-breaking instructions. In case of an emergency, the investigator has the sole responsibility for determining if unblinding of a participant's intervention assignment is warranted. Participant safety must always be the first consideration in making such a determination. If the investigator decides that unblinding is warranted, the investigator should make every effort to contact GSK prior to unblinding a participant's intervention assignment unless this could delay emergency treatment of the participant. If a participant's intervention assignment is unblinded GSK must be notified within 24 hours after breaking the blind. The date and reason that the blind was broken must be recorded in the source documentation and CRF, as applicable.

- If GSK personnel are not contacted before the unblinding, the investigator must notify GSK as soon as possible after unblinding, but without revealing the intervention assignment of the unblinded participant, unless that information is important for the safety of participants currently in the study.
- The date and reason for the unblinding must be fully documented in the CRF
- A participant will be withdrawn if the participant's intervention code is unblinded by the investigator or treating physician. The primary reason for discontinuation (the event or condition which led to the unblinding) will be recorded in the CRF. The participant will be followed up for safety monitoring if treatment was received.
- GSK's Safety and Medical Governance (SMG) staff may unblind the intervention assignment for any participant with an SAE. If the SAE requires that an expedited regulatory report be sent to one or more regulatory agencies, a copy of the report, identifying the participant's intervention assignment, may be sent to investigators in accordance with local regulations and/or GSK policy.

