5. CONSIDERATIONS FOR DATA ANALYSES AND DATA HANDLING CONVENTIONS

5.1. Study Treatment & Sub-group Display Descriptors

Treatment Group Descriptions			
RandAll NG		Data Displays for Reporting	
Code	Description	Description	Order in TLF
A	3 mg/kg IV GSK3858279	GSK3858279	2
P	Placebo	Placebo	1

Treatment comparisons will be displayed as follows using the descriptors as specified:

1. GSK3858279 vs Placebo

For treatment sequence displays:

Treatment Group Descriptions			
RandAll NG		Data Displays for Reporting	
Code	Description	Description	Order in TLF
A/P/P	3 mg/kg IV GSK3858279 – Placebo – Placebo	GSK3858279-Placebo-Placebo	2
P/A/A	Placebo – 3 mg/kg IV GSK3858279 – 3 mg/kg IV GSK3858279	Placebo- GSK3858279- GSK3858279	1
		Total	3

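### A participant unblinded by the investigator must be withdrawn, but his replacement inherits the same sequence, so the site can know part of the replacement's allocation before he is dosed

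*Protocol*

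**What the plan says.** Four provisions bear on this.

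- **Withdrawal after a code break.** Protocol 6.3.2: "A participant will be withdrawn if the participant's intervention code is unblinded by the investigator or treating physician". The rule is limited to code breaks by those two roles.
- **Replacement.** Protocol 1.1 says that after a premature discontinuation "additional replacement participants may be randomized at the discretion of the Sponsor and in consultation with the Principal Investigator". It continues: "Replacement participants will be assigned to the same treatment sequence as the participant they are replacing", again subject to sponsor discretion and consultation with the Principal Investigator. Protocol 4.2 repeats the rule ("Replacement participants will be assigned to the same treatment sequence as the participant that they are replacing"), and so does SAP 12.7.1.
- **Concealment of sequences.** Protocol 6.3.1: "The exact sequences will be blinded to the blinded investigator site staff and participants to prevent bias". Allocation is central, through RAMOS NG, and stratified by morning or afternoon testing.
- **Sequences in use.** SAP 5.1 lists two: active drug followed by placebo twice ("GSK3858279 – Placebo – Placebo") and its mirror image, P/A/A. The protocol says only that the order is randomised.

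There is one centre (Protocol 4.1). Neither document exempts an unblinded participant from same-sequence replacement, gives his replacement a fresh number, or keeps from the site who is replacing whom.

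**The concern.** Each rule is ordinary alone. Together they form a chain: the investigator breaks a code, the participant must leave, a replacement may be recruited at the same site, and he is given the sequence just exposed. The Principal Investigator is consulted about the replacement, so the link between the two men is visible to the site. This works against the aim stated in Protocol 6.3.1.

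Two safeguards are at stake. The first is allocation concealment: site staff could know a candidate's treatment in at least one period while still judging his eligibility. The second is investigator blinding during the pain tests. The primary endpoints are thresholds that the volunteer signals himself, by button for heat and by eVAS slider for cold and electrical pain (Protocol 10.7.1), with site staff present and giving instructions. Expectation conveyed by staff could shift them. Under the MITT definitions in Protocol 9.3 and SAP 4, such a replacement enters the primary analysis like anyone else once he has PainCart data in two periods.

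**Working it through.** The plan states no figure for this point, so the check is whether the chain holds on the text, how much becomes known, and how much data one case represents.

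**1. The chain.** Code break by the investigator or treating physician → mandatory withdrawal (Protocol 6.3.2) → optional replacement (Protocol 1.1 and 4.2) → same sequence (Protocol 1.1 and 4.2, SAP 12.7.1) → same site (Protocol 4.1). Nothing in either document breaks this chain.

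**2. What becomes known.** Protocol 6.3.2 speaks of the intervention assignment and does not say whether a code break reveals one period or the whole sequence. Take the smaller disclosure, one period.

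- *Site knows the SAP 5.1 list {A/P/P, P/A/A}.* The two sequences differ in every period, so any one period identifies the sequence. All 3 of 3 periods are known.
- *Site does not know the list.* Assume that it regards all six orders with both treatments as equally likely. The matching period is still known for certain. If period 1 is A, the candidates are AAP, APA and APP. Then P(period 2 = P) = 2/3 and P(period 3 = P) = 2/3, against 1/2 with no information. The average chance of a correct guess per period is (1 + 2/3 + 2/3)/3 = 77.8%, against 50%.
- *Same assumption, but periods 1 and 2 are both revealed.* The sequence is fully determined for AAP and PPA, which is 2 of 6 = 1/3 of cases. Otherwise period 3 is a coin toss. The average is (1 + 1 + [1/3 × 1 + 2/3 × 1/2])/3 = 88.9%.

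**3. Weight of one case.** This assumes that the replacement completes all three periods.

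| Endpoint | Completers planned (Protocol 9.2) | Share of participant-periods | Post-dose sessions |
|---|---|---|---|
| Cold pressor, electrical | 24 | 3/72 = 4.2% | Days 1, 2, 8, 15, twice each: 8 × 3 = 24 |
| UVB irradiated skin | 15 | 3/45 = 6.7% | Days 1, 2, 8, twice each: 6 × 3 = 18 |

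The UVB count is lower because irradiated skin is not tested on Day 15 (Protocol 1.3.2, SAP 12.6.3).

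**4. How often.** The documents give no expected number of code breaks or replacements. The planned 30 already carry the 20% dropout allowance: 24/(1 − 0.20) = 30. That reduces the need for replacements.

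**The case against.** The strongest reply is that the event is rare and the sponsor can already avoid it. It needs an emergency code break in a healthy volunteer, followed by a decision to replace him. Replacement is optional, and the discretion wording follows the same-sequence sentence, so the sponsor could arguably decline to reuse the sequence. This stands as a limit on frequency. It does not close the gap, because no text tells the sponsor to act differently in this case.

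Several stronger readings are tempting, and the documents do not support them.

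- *Every broken code leads to withdrawal.* Protocol 6.3.2 attaches mandatory withdrawal only to unblinding by the investigator or treating physician. Unblinding by the sponsor's safety staff carries no such rule.
- *All three periods are always exposed.* That requires the site to know the two-sequence list. The list is in the SAP's display table, is meant to be hidden from site staff, and is not shown to be held by the site.
- *The replacement is neither randomised nor blind.* His sequence was generated at random and he may remain blind. He signals his own thresholds under device-controlled stimuli and receives both treatments. Nothing says that the person who broke the code runs the tests. What is lost is concealment and investigator blinding.
- *A hypersensitivity reaction exposes the sequence in the same way.* That is a guess, not knowledge, and it is open in any blinded trial.
- *Safety reports should omit the assignment.* Protocol 6.3.2 says that "a copy of the report, identifying the participant's intervention assignment, may be sent to investigators in accordance with local regulations and/or GSK policy". Those rules lie outside this plan. The case of a participant who continues after such a report is also narrow, since Protocol 7.2 requires withdrawal for several serious events and allows it for others.

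Some traceability already exists: SAP Listing 5 shows participants whose blind was broken, and SAP 4 provides for a population-exclusion meeting before unblinding. Neither links blind breaks to replacements.

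**Conclusion.** The gap is real. As written, the rules allow the investigator to know a replacement's treatment in at least one period before his first infusion, and in all three if the site knows the sequence list. Its likely effect on the results is small: 4.2% of the completer data per case for cold pressor and electrical pain, and 6.7% for UVB. The number of cases is unknown and is assumed to be very small, possibly zero. The conclusion rests on the replacement rule being applied as worded and on the site knowing whom the new participant replaces. SAP 1.1 records that the study was terminated for not meeting the futility threshold, so for this study the question is now one of reporting. The rule itself matters for any later study that reuses the wording.

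**What to change.** **Rule.** In Protocol 1.1, Protocol 4.2 and SAP 12.7.1, add one sentence: if the withdrawn participant's assignment became known to anyone at the site, the replacement takes the next unused randomisation number in the same AM/PM stratum instead of the withdrawn participant's sequence.

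*Cost:* the two sequences may end one or two participants out of balance. This is minor, since the primary model in SAP 7.1.5.1.1 includes treatment and study period. The schedule must hold spare numbers in each stratum; the documents do not state its length.

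**Report for this study.** Cross-check Listing 5 against the replacements and state the count, even if it is zero. If any replacement took over the sequence of an unblinded participant, repeat the three primary analyses without him and show the results beside the main ones.

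*Cost:* one reconciliation and, only if a case exists, one additional run per primary endpoint, with slightly lower precision.

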1.2. Schema

Figure 1 Study Design Schematic

[figure not shown]

Figure 2 Visit schematic

[figure not shown]
[figure not shown]

Figure 3 Study Period Details

* Required only in UVB-MITT population

** Optional assessments/study day applicable to UVB-MITT volunteers only

1.3. Schedule of Activities (SoA)

1.3.1. Screening and follow-up

Procedure	Screening (up to 28 days before Day 1)		Follow-up check 36±4 days post last dose	Final follow-up 56±4 days post-last dose	Notes
	Part 1	Part 2			
Out-patient visit	X	X		X	Optional in-clinic stay for participants at the discretion of investigator.
Phone call			X		AE collection - may be out-patient visit at discretion of Investigator for additional checks
Informed consent	X				
Severe acute respiratory syndrome SARS-CoV-2 PCR test or rapid antigen test	X			X	
Temperature check	X	X		X	
Inclusion and exclusion criteria	X				Recheck clinical status before randomization and/or 1st dose of study intervention.
Demography	X				
Full physical examination including height and weight.	X				Weight at screening is used for determination of dose
Fitzpatrick Skin Type	X				Assessments for UVB-MITT population only Assessment to determine applying MED application
Echocardiogram	X				
Medical history (includes substance usage)	X				Substances: Drugs, Alcohol, tobacco and caffeine
Current medical conditions	X				
HIV, Hepatitis B and C	X				
Haematology, clinical chemistry (include liver chemistries) and urinalysis	X			X	Including Troponin-T (hs)
NT-proBNP	X			X	
UrDrug, BrAlc	X			X	
12-lead ECG	T			X	T = Triplicate X = Single
Vital signs	X			X	

Procedure	Screening (up to 28 days before Day 1)		Follow-up check 36 ± 4 days post last dose	Final follow-up 56 ± 4 days post-last dose	Notes
	Part 1	Part 2			
PainCart training	[X]	[X]			May be performed during either part 1 or part 2 (not both)
Minimal Erythema Dose (MED) application		X			Assessments for UVB-MITT population only. Exposure to pre-determined 6 ascending doses of UVB radiation. MED application will be the final assessment on Part 1 of Screening and will only be completed after confirmation of eligibility from available results, e.g. lab data, echocardiogram results may not be available.
MED assessment			X		Assessments for UVB-MITT population only. 24 hours (± 2 hours) after UV exposure
AE/SAE review	X	X	X	X	

- An echocardiogram performed within 3 months prior to first dosing is acceptable for enrolment into the study
- MED determination performed within 6 weeks prior to first dosing is acceptable for enrolment into the study

